Appendix B Modified Rankin Scale

CONFIDENTIAL INFORMATION MD133246 Protocol Template Revision#: 1 Doc Type: GC

MODIFIED RANKIN SCALE

CHECK ONE

GRADE ONLY

Patient's name:

Hospital number:

0	•••••	No symptoms at all.
1		No significant disability despite symptoms: Able to carry out all usual activities.
2		Slight disability.
3		Moderate disability: Requiring some help but able to walk without assistance .
4		Moderate to severe disability: Unable to walk without assistance and unable to attend to own bodily needs without assistance.
5		Severe disability: Bedridden, incontinent and requiring constant nursing care and attention.
6		Death.

DESCRIPTION

# 1.0 Introduction

This Statistical Analysis Plan (SAP) describes the statistical analyses planned to address the objectives of GCS 10-08. It summarizes the analyses that will be performed to determine the safety and effectiveness of the GORE® Carotid Stent for the treatment of carotid artery stenosis in patients at increased risk for adverse events from carotid endarterectomy. This SAP outlines tables, figures, and listings that are included in reports for the GCS 10-08 clinical study.

# 2.0 Study Design

#### 2.1 **Objectives**

#### 2.1.1 Primary Objective

The primary objective of this study is to evaluate the safety and efficacy of the GORE® Carotid Stent for the treatment of carotid artery stenosis in patients at increased risk for adverse events from carotid endarterectomy.

#### 2.1.2 Secondary Objective(s)

No secondary objectives were specified for this study.

#### 2.2 Study Treatment Arms

#### 2.2.1 Test Arm and Test Device

The test arm will consist of consecutively enrolled, prospectively treated and followed subjects who satisfy all of the inclusion and none of the exclusion criteria. Test subjects will be treated with the GORE® Carotid Stent, hereafter referred to as the *test device*.

#### 2.2.2 Control Arm

This is a single-arm clinical study with no concurrently enrolled control subjects for comparison. The comparator for the primary hypothesis test will consist of a performance goal developed from published carotid endarterectomy outcomes in a high-risk population.

#### 2.3 Enrollment

A patient is considered an enrolled subject in the study when the test device enters the patient's vasculature, also referred to as "test device attempted." Enrollment of the subject is indicated in the study data system by a response of Yes to Question 18 of the Procedure CRF, "Was a GORE® Carotid Stent introduced into the subject's anatomy?"

#### 2.4 Design Summary

This is a prospective, multicenter, single-arm, clinical study comparing outcomes with the GORE® Carotid Stent (test device) to a performance goal.

A maximum of 50 investigative sites in the U.S., Europe, and Japan will participate in this study. Three hundred twelve (312) subjects will be enrolled in this study with a limit of 40 subjects enrolled at any single site. The anticipated accrual rate is approximately 15-20 subjects per month for a total accrual period of approximately 18-24 months.

Patients may be enrolled into the clinical study provided all inclusion and no exclusion criteria are met. Subjects will be evaluated through hospital discharge and return for follow-up visits at 30 days, 6 months, and 1, 2, and 3 years post-procedure.

The total study duration from start-up to close-out is expected to be 60 months. A full analysis of all relevant data will be submitted to the FDA and PMDA for PMA and Shonin approval upon completion of the primary endpoint analysis.

#### 2.5 Study Endpoints

#### 2.5.1 Primary Endpoint

The primary study endpoint is a composite of Major Adverse Events (MAE) defined as death, any stroke, or myocardial infarction (MI) through 30 days post-index procedure, and ipsilateral stroke between 31 days and 1 year (365 days). All primary endpoint events will be adjudicated and determined by the study Clinical Events Committee (CEC).

#### 2.5.2 Secondary Endpoints

Stent Technical Success: Successful deployment of the test device.

**EPD (Embolic Protection Device) Technical Success:** Technical success for the GORE® Embolic Filter is defined as: EPD delivered, placed, and retrieved without requiring assisting interventional methods.

**Procedure Success:** Stent Technical Success, <30% residual angiographic stenosis by visual assessment post-procedure in the target lesion and no in-hospital (pre-discharge) Major Adverse Event.

**30-Day Major Adverse Events:** Composite of death, any stroke, or myocardial infarction through 30 days post-index procedure.

**In-stent Restenosis:** Measured as percent stenosis at follow-up evaluation within the stented lesion or within 5 mm proximal or distal to the stent. Additionally will assess percent of subjects with stenosis  $\geq$ 50% by ultrasound and  $\geq$ 80% by angiographic evaluation.

**Target Lesion Revascularization (TLR):** any clinically driven revascularization procedure of the original treatment site, including angioplasty, stenting, endarterectomy, or thrombolysis, performed to open or increase the luminal diameter inside or within 5 mm of the previously treated lesion.

[figure not shown]
# $H_0 = P_a + P_c \ge$ $H_1 = P_a + P_c <$

#### 2.6 Statistical Hypotheses

 ┛─┼╴┨╴┼╌╻	╺╶┼╌╏┛╶╌┼╼┨┓╌	┼╍┻╍┼╌╻┛╘╍╌╢

[figure not shown]

$\left[ \begin{array}{c} 1 \\ 1 \\ 1 \\ \sqrt{100^2} \\ 1 \\ 1 \\ 1 \\ \sqrt{100^2} \\ 1 \\ 1 \\ 1 \\ 1 \\ 1 \\ 1 \\ 1 \\ 1 \\ 1 \\ $

[figure not shown]

# 3.0 Study Data Collection

#### 3.1 Study Data Collection Intervals

Figure 2 below shows expected evaluations depending on a subject's enrollment status and technical outcome.

#### Figure 2. Study Procedures and Evaluation Schema

#### 3.2 Study Interval Windows

Subjects with successful test device implant will return for follow-up at 30 days, 6 months, 1, 2 and 3 years. Subjects considered Technical Failures (test device attempted but not implanted) are only required to complete a 30-day follow-up and will have then completed the study. All intervals are calculated from the index procedure. The 6-Month visit target is 180 days. The yearly visits are calculated on a calendar year from index procedure.

30 Days	6 Months	1 Year	2 Years	3 Years
30±7 days	180±14 days	365±30 days	730±45 days	1,095±45 days

#### 3.3 Data and Safety Monitoring Board

An independent Data and Safety Monitoring Board (DSMB) will oversee conduct of the study. The DSMB will review accumulating study safety data on a regular basis and will advise the Sponsor regarding the continuing safety of study subjects as well as the continuing validity and scientific merit of the study. The DSMB will be comprised of an interdisciplinary team of at least 3 members (2 voting physicians, and one voting statistician) with pertinent expertise in carotid stenting who are not directly involved in the conduct of the

study. The members will be compensated for their involvement in the DSMB, including reimbursement for reasonable travel expenses to attend meetings.

This committee will operate under prespecified procedures as outlined in the DSMB Charter in accordance with the FDA's Guidance for Clinical Trial Sponsors on the Establishment and Operation of Clinical Trial Data Monitoring Committees. The DSMB will be responsible for conducting periodic reviews of aggregate data on a prescribed basis. The frequency of data review and other roles and responsibilities of the DSMB will be specified in the DSMB Charter.

Based on the safety data review, the DSMB will make recommendations to the Sponsor. Recommendations may include study continuation with or without major or minor modifications, temporary suspension of enrollment and / or study intervention until some uncertainty is resolved. All final decisions regarding study modifications rest with the Sponsor.

#### 3.4 Clinical Events Committee

An independent Clinical Events Committee (CEC) will review potential primary endpoint events and adjudicate events based on endpoint definitions in the study protocol. The CEC will be comprised of an interdisciplinary team with pertinent knowledge in carotid stenting or the cardiovascular and/or nervous system who are not directly involved in the conduct of the study. The members will be compensated for their involvement in the CEC, including reimbursement for reasonable travel expenses to attend meetings.

This committee will operate under prespecified procedures as outlined in the CEC Charter. The adjudication process will be initiated after a potential primary endpoint event is reported by the site.

#### 3.5 Site Enrollment Restrictions

A maximum of 50 investigative sites in the U.S., Europe, and Japan will participate in this study. Three hundred twelve (312) subjects will be enrolled in this study with a limit of 40 subjects enrolled at any single site. The anticipated accrual rate is approximately 15-20 subjects per month for a total accrual period of approximately 18-24 months.

#### 3.6 Core Labs

This study will utilize a carotid duplex ultrasound core lab and an angiographic core lab. Specific administrative information on these core labs can be found in the study protocol.

[figure not shown]
# 4.0 Statistical Analyses

#### 4.1 Analysis Sets

The primary endpoint will be analyzed both on an intent-to-treat basis and on a per-protocol basis. The primary analysis set for testing of the primary endpoint is the per-protocol analysis set.

#### 4.1.1 Intent-To-Treat (ITT) Analysis Set

The ITT analysis set is defined as all enrolled subjects (test device attempted) with adequate informed consent, regardless of whether or not the test device was implanted. Because technical failures (test device attempted but not implanted) are followed only to 30 days, this set will be used in the analysis of safety endpoints (major, serious, and

nonserious adverse events) to 30 days and secondary endpoints evaluated at procedure, discharge, and 30 days.

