Post-procedural extracranial and intracranial angiograms should be performed in accordance with the angiographic core laboratory specifications.

GORE® Carotid Stent Technical Failure

If a GORE® Carotid Stent is not implanted due to technical reasons, another locally approved carotid stent may be used to complete the procedure. Subjects who do not have a successful GORE® Carotid Stent implant during the index procedure will be considered technical failures. Technical failure subjects only require follow-up through 30 days post-procedure and will then have completed the study.

Device failures and malfunctions will be documented on the Stent Assessment case report form and the study device will be returned to W. L. Gore and Associates, Inc. for analysis. Instructions for returning the study device will be provided in the study binder supplied by W. L. Gore and Associates, Inc.

Examples of when to return device malfunctions include (but are not limited to):

- Device fails to perform as intended
- Device physically deforms or breaks, even if due to user error
- Packaging is defective

Any opened but unused device will need to be returned to W. L. Gore and Associates, Inc.

GORE CONFIDENTIAL INFORMATION MD133246 Protocol Template Revision#: 1 Doc Type: GC

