5.11. Follow-Up

Subjects with successful GORE® Carotid Stent implant will return for follow-up at 30 days, 6 months, 1, 2 and 3 years. Subjects considered Technical Failures (no GORE® Carotid Stent implant) are only required to complete a 30 day follow-up and will have then completed the study.

The following assessments are required for each follow-up visit (unless indicated otherwise):

- Exam and vital signs
- NIHSS
- Modified Rankin Scale
- Carotid Duplex Ultrasound of target vessel
- Concomitant medications (antiplatelet or anticoagulant therapy) assessment
- Adverse events assessment

GORE CONFIDENTIAL INFORMATION

Follow-up Visit Windows

The follow-up visits should be completed within an acceptable time frame and in accordance with the protocol defined visit windows. All intervals are to be calculated from the index procedure. The 6-Month visit target is 180 days. The yearly visits are calculated on a calendar year from index procedure.

30 Days	6 Months (180 Days)	1 Year	2 & 3 Years
\pm 7 days	\pm 14 days	\pm 30 days	\pm 45 days

If the visit is not able to be completed during these windows the visit should be completed as soon as possible; however, it will be considered a protocol deviation and should be reported per local IRB policy.

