10.4.3. Analysis Sets

The primary endpoint will be analyzed both on an intent-to-treat basis and on a perprotocol basis. The primary analysis set for testing of the primary endpoint is the perprotocol analysis set.

Intent-To-Treat (ITT) Analysis Set

The ITT analysis set is defined as all enrolled subjects with adequate informed consent, regardless of whether the study stent was implanted. Because technical failures (test device attempted but not implanted) are followed only to 30 days, this set will be used in the analysis of safety endpoints (major, serious, and nonserious adverse events) to 30 days and secondary endpoints evaluated at procedure, discharge, and 30 days.

Per-Protocol Analysis Set (Primary Analysis Set)

For per-protocol analysis, only subjects who had the study stent implanted in the target vessel and had no major protocol deviations will be included in the analysis. Major protocol deviations are defined as protocol deviations with a level of seriousness such that inclusion of the subject(s) would unacceptably bias the primary endpoint analysis. An example of a major protocol deviation might be failure to satisfy eligibility criteria to a degree where the subject does not fit the underlying scientific model for the treatment.

The per-protocol set will be used for the primary analyses of the primary endpoint. Ideally, this analysis set will consist of all subjects from the ITT set with technical success (test device implanted).

The Per-Protocol set will be used in additional analyses of the primary and secondary endpoints.

The primary safety and efficacy endpoints will also be analyzed controlling for the following baseline covariates: age, sex, and race/ethnicity.

Additional subgroup analyses may be performed based on variables identified to be significant predictors (p-value<0.05) in multivariate analyses.

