**30-Day Major Adverse Events:** Composite of death, any stroke, or myocardial infarction through 30 days post-index procedure. It will be calculated as a subject-based binomial proportion. The numerator will be the count of subjects who experience CEC-adjudicated MAE through 30 days post-index procedure. The denominator will be the count of subjects free of MAE through 30 days post-index procedure and with clinical follow-up of at least 23 days post-index procedure, plus the count of subjects in the numerator.

**In-stent Restenosis:** Measured as percent stenosis at follow-up evaluation within the stented lesion or within 5 mm proximal or distal to the stent. Additionally will assess percent of subjects with stenosis  $\geq$ 50% by ultrasound and  $\geq$ 80% by angiographic evaluation.

The text above is taken verbatim from the clinical protocol. There are three separate endpoint measures implied by this description, defined below:

**In-stent Percent Diameter Stenosis:** calculated as a subject-based categorical frequency distribution of "In Stent Stenosis Category" as reported on the Carotid Artery Duplex Scan CRF among subjects with a valid, nonmissing value for this item.

The stenosis categories are the following:

- Patent
- 50-79%
- >70%
- 80-99%
- Occluded

**In-stent Restenosis By Ultrasound:** calculated as a subject-based binomial proportion. The numerator will be the count of subjects with stenosis ≥50% by ultrasound (indicated as any valid, nonmissing stenosis category other than "Patent") as reported on the Carotid Artery Duplex Scan CRF. The denominator will be the count of subjects with a valid, nonmissing value for this item.

**In-stent Restenosis By Angiography:** calculated as a subject-based binomial proportion. Restenosis failures will be indicated by an angiography core lab-adjudicated stenosis of ≥80% as reported on the Angio Core Lab Adjudication CRF. Not all subjects will have a follow-up angiography performed, only those whose ultrasound-determined stenosis and/or clinical symptoms provokes an angiography by the investigator. The denominator will be the count of subjects with a valid, nonmissing value for ultrasound-determined stenosis.

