**Target Lesion Revascularization (TLR):** any clinically-driven revascularization procedure of the original treatment site, including angioplasty, stenting, endarterectomy, or thrombolysis, performed to open or increase the luminal diameter inside or within 5 mm of the previously treated lesion. This will be calculated using Kaplan-Meier (K-M) survival analysis. Events will be subjects who experience TLR as reported on the Reintervention CRF. Censored observations will be subjects free of TLR. K-M estimates corresponding to the study follow-up intervals will be reported, as well as a graph of the entire survival distribution.

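### The 30-day in-stent restenosis results default to the ITT set with no implant condition, so they can include subjects who carry a substituted, non-study stent

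*SAP*

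**What the plan says.** **Analysis set.** SAP 4.1.1 defines ITT as all enrolled subjects, meaning those in whom the test device was attempted, "regardless of whether or not the test device was implanted". It uses this set for major, serious and "nonserious adverse events) to 30 days and secondary endpoints evaluated at procedure, discharge, and 30 days". Protocol 10.4.3 has the same rule: "this set will be used in the analysis of safety endpoints (major, serious, and nonserious adverse events) to 30 days and secondary endpoints evaluated at" those same three occasions. The reason given is that technical failures are followed only to 30 days.

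**Technical failures.** Protocol 5.8: "If a GORE® Carotid Stent is not implanted due to technical reasons, another locally approved carotid stent may be used to complete the procedure". Protocol 5.11 and SAP 3.2 require these subjects to attend the 30-day visit, after which they have completed the study. The Protocol 5.11 list of assessments for each follow-up visit, which applies unless otherwise indicated, includes "Carotid Duplex Ultrasound of target vessel". The schedule in Protocol 5.2 marks duplex at 30 days and shows no exception for technical failures.

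**In-stent restenosis.** SAP 4.4 derives three measures. The stenosis distribution and the ultrasound proportion come from the in-stent stenosis category item on the duplex CRF. For the ultrasound proportion: "The denominator will be the count of subjects with a valid, nonmissing value for this item". The angiographic proportion uses subjects with a valid ultrasound stenosis value as its denominator. None of the three names an analysis set or requires that the stent be the test device.

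**Target lesion revascularization (TLR).** SAP 4.4 defines it by the original treatment site and analyses it by Kaplan-Meier: "K-M estimates corresponding to the study follow-up intervals will be reported, as well as a graph of the entire survival distribution". No analysis set is named here either.

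**The concern.** ITT is the natural set for stent technical success, embolic protection success, procedure success and 30-day MAE, because a failed attempt is part of what those endpoints measure. In-stent restenosis is different: it describes an implanted stent, and the study's objective is to evaluate one particular stent. A programmer who follows SAP 4.1.1 and 4.4 literally would take every ITT subject with a completed 30-day stenosis item. A technical failure with a substituted stent and a completed item would then enter the 30-day result. If the scan is patent, the subject adds to the denominator. If it shows 50% or more, the subject also adds to the ultrasound numerator.

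From 6 months onward this cannot happen, because those subjects have left the study. The 30-day figure and the 6-month to 3-year figures would then describe slightly different groups, and nothing in the table would show it.

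**Working it through.** The plan states no figure on this point, so there is none to reproduce. The check has two parts.

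**Part 1: can a non-study stent reach the 30-day result?**

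1. The set for 30-day secondary endpoints is ITT (SAP 4.1.1, Protocol 10.4.3).
2. ITT keeps technical failures (SAP 4.1.1).
3. For a technical failure, "another locally approved carotid stent may be used to complete the procedure" (Protocol 5.8). This is permitted, not certain.
4. The 30-day visit is required for them, and duplex is among the listed assessments (Protocol 5.11 and 5.2).
5. Entry to the restenosis result needs only a valid, nonmissing item (SAP 4.4).

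No step excludes or separates these subjects. The route is open whenever a substitute stent was placed and the item was completed.

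**Part 2: how large could the effect be?**

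Inputs:
- N = 312 planned subjects (SAP 2.4), all taken as evaluable at 30 days.
- Technical failure rate: not given, assumed 1%, 2%, 3% or 5%, so k = 3, 6, 9 or 16.
- 30-day restenosis rate in implanted subjects, r_I: assumed 1% or 3%.
- 30-day restenosis rate in technical failures, r_F: assumed 0% to 20%.

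Formulas:
- ITT rate = [r_I × (312 − k) + r_F × k] / 312
- Shift from the implanted-only rate = (k / 312) × (r_F − r_I)
- One event in a technical failure adds 1/312 = 0.32 points.

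Shift in percentage points:

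| Failure rate | k | Implanted | r_I 1%, r_F 0% | r_I 1%, r_F 20% | r_I 3%, r_F 0% | r_I 3%, r_F 20% |
|---|---|---|---|---|---|---|
| 1% | 3 | 309 | −0.01 | +0.18 | −0.03 | +0.16 |
| 2% | 6 | 306 | −0.02 | +0.37 | −0.06 | +0.33 |
| 3% | 9 | 303 | −0.03 | +0.55 | −0.09 | +0.49 |
| 5% | 16 | 296 | −0.05 | +0.97 | −0.15 | +0.87 |

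The two extremes by hand: (16/312) × (0.20 − 0.01) = +0.97 points, and (16/312) × (0 − 0.03) = −0.15 points.

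As whole counts, take 16 technical failures and 3 restenoses among 296 implanted subjects. The implanted-only rate is 3/296 = 1.01%. The ITT rate is 3/312 = 0.96%, 4/312 = 1.28% or 5/312 = 1.60% with 0, 1 or 2 restenosed substitute stents. The last case needs 2 of 16 (12.5%) substitute stents restenosed by day 30, which is a deliberately severe assumption.

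**The case against.** **Material that is not visible may settle it.** SAP 3.1 says that Figure 2 shows the expected evaluations by technical outcome. Neither that figure nor the protocol's schema can be read in the public copy, and the CRF is not shown. The stenosis item might be left blank when no study stent is present. This stands as a limit: the text permits the mixing, but whether it occurs depends on the form. A line in SAP 4.4 would settle it either way.

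**An implanted-only analysis is already planned.** Protocol 10.4.3 says the per-protocol set will also be used for further analyses of the secondary endpoints, and that set requires the study stent. This stands in part. Those analyses are additional to the ITT assignment and do not replace it, the SAP does not carry the sentence over, and the per-protocol set also removes major deviations, so it is not simply the implanted group.

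**Stronger readings the documents do not support.**
- A reader might infer that another manufacturer's results are credited to the study stent. The plan does not say so. A substitute stent is only permitted, its manufacturer is not stated, a technical failure may have no stent at all, and the SAP is silent on attribution.
- A reader might infer that the reported cumulative TLR could fall after 30 days. That would need an ITT point at 30 days joined to per-protocol points later, and no section asks for this. In one Kaplan-Meier curve, technical failures who leave at about day 30 are censored, and the cumulative estimate cannot fall.
- A reader might infer that TLR must be limited to implanted subjects. TLR is defined by treatment site, so keeping failed attempts is ordinary ITT. Removing them would condition on procedural success and could hide early re-intervention after a failed deployment. That choice is open to debate and is not an error.

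**Conclusion.** The point holds for in-stent restenosis at 30 days. Under the stated rules, the stenosis distribution and both restenosis proportions at that visit can include technical failures who have a substituted stent and a completed stenosis item, whereas later visits cannot.

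The consequence is minor. With all 312 subjects evaluable and the assumed failure and event rates above, the 30-day rate moves by at most about one percentage point, and by a few tenths or less in most of the cases tried. The true technical failure rate is not in the documents, so this is a range and not an estimate. Secondary endpoints are descriptive with no hypothesis tested (SAP 4.4), and the primary test uses the per-protocol set, so the study's main conclusion is not at risk.

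For TLR the only gap is that no analysis set is named for the curve.

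**What to change.** 1. In SAP 4.4, state that In-stent Percent Diameter Stenosis and both in-stent restenosis proportions are computed at every time point, including 30 days, in subjects with the test device implanted.
2. In SAP 4.1.1 and Protocol 10.4.3, except these three measures from the rule that sends 30-day secondary endpoints to ITT.
3. List the 30-day duplex results of technical failures separately.
4. In SAP 4.4, name the single analysis set used for the whole TLR Kaplan-Meier curve.

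The cost is a few sentences and one short listing, with no new data. The one downside is that the few technical failures leave the 30-day restenosis denominator, but they stay visible in the listing.
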